- While FdCyd + THU has shown preliminary evidence of activity in early phase trials not all patients show clinical response. The establishment of a radiolabeled form to image the biodistribution *in vivo* at baseline and during therapy may provide insight into the distribution of the therapeutic drug.
- The first step in the development of such an *in vivo* marker is to determine the biodistribution and safety of the radiolabeled form.

Objectives:

- Determine the safety of [F-18]-5-fluoro-2'-deoxycytidine (FdCyd) administered intravenously with administration of tetrahydrouridine (THU).
- Estimate the radiation dosimetry of [F-18]-FdCyd in humans.

Eligibility:

- Only patients enrolled in NCI Phase II Study evaluating FdCyd with THU (NCI Protocol # 09-C-0214 (CTEP# 8351) or NCI Protocol #12-C-0066 (CTEP# 9127)) at the NIH Clinical Center will be eligible to participate in this study).
- Patients must have a target lesion ≥ 10 mm
- May not be pregnant or lactating; must be ≤ 350 lbs; and may not have known allergy to FdCyd or contraindications to PET/CT imaging.

Design:

- There are two arms to this study
 - The first arm will be patients enrolling in the therapeutic Phase II 5-FdCyd/THU study (NCI Protocol # 09-C-0214 (CTEP# 8351) in the NCI Developmental Therapeutics Clinic
 - The second arm will be patients enrolling in the Phase I 5-FdCyd/THU study (NCI Protocol #12-C-0066 (CTEP# 9127)) in the NCI Developmental Therapeutics Clinic.
- Patients will undergo an initial [F-18]-FdCyd + THU PET/CT imaging prior to therapeutic dosing on study NCI Protocol # 09-C-0214 (CTEP# 8351) or NCI Protocol

Abbreviated Title: [F-18] FdCyd Imaging

Version Date: 03-09-2015

Protocol Number: CTEP 8865, NCI 12-C-0014

#12-C-0066 (CTEP# 9127). Repeat imaging will be performed while the patient is receiving FdCyd + THU therapy under the parent therapeutic protocol. This imaging must be completed 2-5 days after cycle start and at least 2 hours after a dose. Upon completion of repeat imaging, patients will be taken off this imaging study 24 hours after the last imaging session.

TABLE OF CONTENTS

Précis..... 3

TABLE OF CONTENTS..... 5

1 INTRODUCTION 7

 1.1 Study Objectives 7

2 Background and Rationale:..... 7

 2.1 [F-18]-5-Fluoro-2'-deoxycytidine (FdCyd)..... 8

 2.2 Tetrahydrouridine (THU)..... 12

 2.3 Rationale..... 12

3 Patient Selection..... 13

 3.1 Eligibility Criteria 13

 3.2 Screening Evaluation..... 14

 3.3 Inclusion of Women and Minorities..... 14

1 INTRODUCTION

1.1 Study Objectives

1.1.1 Primary Objectives:

- 1.1.1.1 To determine the safety of [F-18]-5-fluoro-2'-deoxycytidine (FdCyd) administered intravenously with administration of tetrahydrouridine (THU)
- 1.1.1.2 To estimate the radiation dosimetry of [F-18]-FdCyd in humans

1.1.2 Secondary Objectives:

- 1.1.2.1 To evaluate the pharmacokinetics of [F-18]-FdCyd via PET/CT
- 1.1.2.2 To evaluate the distribution of FdCyd in tumorous and non-tumorous tissue

2 BACKGROUND AND RATIONALE:

5-fluoro-2'-deoxycytidine (FdCyd), administered along with tetrahydrouridine (THU; an inhibitor of cytidine/deoxycytidine deaminase), has shown superior anti-tumor activity as compared with 5-fluorouracil in pre-clinical models. Following administration of FdCyd, it is phosphorylated to 5-fluoro-2'-deoxycytidylate (FdCMP) by deoxycytidine kinase and the nucleotide deaminated to FdUMP by deoxycytidylate (dCMP) deaminase. The activity of dCMP deaminase is reported to be higher in human malignancies than in normal tissues, which may result in selective cytotoxicity. FdCyd is an inhibitor of DNA methyltransferase (DNMT) and DNA methylation, resulting in re-expression of genes silenced by DNA hypermethylation. Co-administration of THU inhibits the metabolism of the parent FdCyd allowing it to circulate in its original form, and intracellularly inhibit DNMT.

The process of intracellular activation creates a charged species that is trapped inside the cell, and since the sensitivity is directly linked to the amount of activated drug that collects inside the cell, the drug itself has very favorable properties as a probe for tumor localization. The biomolecular literature indicates that the pathways for intracellular uptake, retention, and activation of 5FdC to nucleotides are subject to substantial variation in human tumors. Thus, information that could guide the selection of tumors that were more likely to be sensitive or resistant to 5FdCyd would potentially aid in its development.

[figure not shown]

Figure 1: NSC 48006, 5-F-deoxycytidine (5FdC) and Tetrahydrouridine (THU)

In general, noninvasive imaging of many pyrimidines has been hindered by the high amounts of background radioactivity produced by catabolism. In the proposed study, co-administration of THU inhibits the catabolism of FdCyd reducing the background.

Abbreviated Title: [F-18] FdCyd Imaging

Version Date: 03-09-2015

Protocol Number: CTEP 8865, NCI 12-C-0014

The radioactive dose is 5 mCi or less at the time of administration.

2.1.3 Toxicity:

The quantity of [F-18]-FdCyd required for imaging is a microdose, and no toxicity is expected to be observed from the radiopharmaceutical. However, patients will be observed particularly for the toxicities noted in the animal and therapeutic studies. Based on the results of animal studies (1), the toxicities of a therapeutic dose of FdCyd are expected to be similar to those produced by 5-FdU and 5-FU, including neutropenia, mucositis, diarrhea, nausea and vomiting. This drug should be considered to have potential carcinogenic and teratogenic effects based on the carcinogenicity/teratogenicity of related drugs and on the teratogenic effects of FdCyd that have been reported in mice, including vertebral malformations, supernumerary limbs, and limb malformations.

During a Phase 1 therapeutic trial, additional toxicities possibly related to the FdCyd/THU were noted at FdCyd doses of 40 mg/m²/day 5 days a week for 2 weeks and above. These toxicities included electrolyte imbalances not immediately corrected with supplementation, elevated liver function tests, and anemia. None of the toxicities to date have had unresolved sequelae.

2.1.4 Pre-clinical Biodistribution for [18F]-FdCyd:

Radiation dosimetry estimates were based on rodent studies performed by IBA (the manufacturer of this radiotracer) under an NCI contract and the results are included in Table 1, and sample images are included in [Figure 3](#). Briefly, the estimated ED for the doses proposed in this study (5 mCi FdCyd) and transmission CT for a total of 2 imaging sessions) is 3.52 rem and the organs receiving the highest doses are the urinary bladder, liver, and kidneys.

Table 1

Radiation Dosimetry and Effective Dose Calculation		
Material:	F-18 FdCyd	
Dose/study	5	mCi
Subject Age:	ADULT	DOSE/STUDY
Organ	rad/mCi	rads
Adrenals	0.019	0.0955
Brain	0.001	0.0065
Breasts	0.004	0.01945
Esophagus¹	0.004	0.02085
Gallbladder Wall	0.031	0.154
Lower Large Intestine	0.038	0.192

Radiation Dosimetry and Effective Dose Calculation		
Material:	F-18 FdCyd	
Dose/study	5	mCi
Subject Age:	ADULT	DOSE/STUDY
Organ	rad/mCi	rads
Small Intestine	0.020	0.0975
Stomach	0.009	0.0459
Upper Large Intestine	0.018	0.091
Colon ²	0.027	0.13443
Heart Wall	0.009	0.04625
Kidney	0.125	0.625
Liver	0.145	0.725
Lungs	0.020	0.1015
Muscle	0.016	0.079
Ovaries	0.036	0.182
Pancreas	0.016	0.081
Red Marrow ³	0.011	0.0555
Bone Surfaces ⁴	0.007	0.03645
Skin	0.006	0.02845
Spleen	0.008	0.04165
Testes	0.026	0.1275
Thymus	0.004	0.02085
Thyroid	0.002	0.0109
Urinary Bladder Wall	1.250	6.25

Radiation Dosimetry and Effective Dose Calculation		
Material:	F-18 FdCyd	
Dose/study	5	mCi
Subject Age:	ADULT	DOSE/STUDY
Organ	rad/mCi	rads
Uterus	0.081	0.405
Salivary Glands ³	0.002	0.0109
REMAINDER AVE	0.036	0.180544444
EFFECTIVE DOSE (rem)		4.42E-01

Notes

[figure not shown]
¹ Since no dose is explicitly tabulated for esophagus, thymus dose is used (as per ICRP 80)

² Colon Dose estimated by $[0.57 (\text{Dose}_{\text{ULI}}) + 0.43 (\text{Dose}_{\text{LLI}})]$ (as per ICRP 80).

³Salivary gland dose is set equal to the thyroid dose

Source: IBA, manufacturer

Figure 3:

[figure not shown]

Abbreviated Title: [F-18] FdCyd Imaging

Version Date: 03-09-2015

Protocol Number: CTEP 8865, NCI 12-C-0014

- a) Typical image of the kidneys after 4 hours (MIP, Axial, sagittal, and coronal at the level of the kidneys)

- b) Same mouse, typical image of the liver at 4 hours (MIP, Axial, sagittal, and coronal at the level of the liver)

As ^{18}F FdCyd is chemically identical to the therapeutic drug FdCyd, the preclinical toxicity data from the therapeutic agent is the same as that for this imaging agent.

2.2 Tetrahydrouridine (THU)

2.2.1 Chemistry and Pharmacology:

THU [C₉H₁₆N₂O₆, mol. wt. 248.2] is an effective inhibitor of Cyt/dCyt deaminase in animals and humans (18, 19). It has a plasma half-life in humans of approximately one hour (19).

2.2.2 Toxicity:

At an average total dose of 750 mg/kg (10 to 50 mg/kg/day for up to 23 days), THU alone was not toxic to humans; THU potentiated the toxicity of araC, but no toxicity occurred with the combination that would not have been expected from araC given alone at an equitoxic dose (20). THU has been administered by three-hour infusion in conjunction with araC without producing toxicities other than those expected from the araC (22).

2.3 Rationale

FdCyd + THU has shown preliminary evidence of clinical benefit in early phase trial and is being evaluated in a phase II trial for the treatment of refractory head and neck, breast, non-small cell lung and transitional cell carcinoma as part of the CTEP 8351 (NCI Protocol # 09-C-0214) trial. However, the clinical benefit so far has been observed in a minority of patients making it important to design a strategy for patient selection. By establishing a method to evaluate the biodistribution of the drug and its ability to be taken up by the tumor cells, achieving intracellular therapeutic concentrations may provide insight into these variable responses.

Abbreviated Title: [F-18] FdCyd Imaging

Version Date: 03-09-2015

Protocol Number: CTEP 8865, NCI 12-C-0014

Currently an oral form of 5-fluoro-2'-deoxycytidine with oral tetrahydrouridine is being tested in a phase I study (CTEP# 9127, NCI Protocol 12-C-0066) in patients with advanced solid tumors. The goal of the protocol is to achieve oral FdCyd plasma concentrations similar to IV administration concentrations. Protocol 12-C-006 (CTEP 9127) is being performed because one of the main limitations of the IV regimen is the number of days and duration of drug administration in each cycle, which requires multiple patient visits. An oral formulation would improve feasibility and compliance; therefore allowing an additional pool of patients that can participate in this study.

The proposed study with the establishment of a radiolabeled form could image the biodistribution at baseline and during therapy in patients receiving the therapeutic drug. The first step in the development of such an *in vivo* marker is to determine the safety of the radiolabeled form and the radiation dosimetry. The resultant pharmacokinetics of [F-18]-FdCyd will subsequently be evaluated both with and without non- radiolabeled FdCyd concurrently administered using PET/CT. Due to rapid metabolism in the absence of a Cyt/dCyd deaminase inhibitor, a trial of single agent [F-18]-FdCyd alone would be irrelevant to the potential clinical utility of this drug. Therefore, the treatment plan of this protocol incorporates a fixed dose of THU which is known to be safe, and to effectively diminish the activity of Cyt/dCyd deaminase in humans (22).

3 PATIENT SELECTION

3.1 Eligibility Criteria

3.1.1 Inclusion Criteria

- 3.1.1.1 Enrolled in the NIH Phase II Clinical protocol evaluating FdCyd with THU (NCI protocol # 09-C-0214 (CTEP# 8351) or NCI protocol #12-C-0066 (CTEP# 9127)) with target lesion measured as ≥ 10 mm with spiral CT scan.
- 3.1.1.2 Written, voluntary, informed consent of the patient must be obtained in compliance with institutional, state and federal guidelines
- 3.1.1.3 For females: Negative serum pregnancy test OR post-menopausal for at least 2 years OR patient has had a hysterectomy

3.1.2 Exclusion Criteria

- 3.1.2.1 Participants with severe claustrophobia unresponsive to oral anxiolytics
- 3.1.2.2 Subjects weighing > 400 lbs (weight limit for scanner table), or unable to fit within the imaging gantry
- 3.1.2.3 Known allergy to FdCyd
- 3.1.2.4 The subject is unable to lie still for ~ 75 minutes
- 3.1.2.5 Pregnant or lactating women. Pregnant women are excluded from this study because the effects of 18F-FdCyd in pregnancy are not known. Because there is an unknown but potential risk for adverse events in nursing infants secondary to administration of 18F-FdCyd in the mother, breastfeeding should be discontinued if the mother receives 18F-FdCyd
- 3.1.2.6 Participants with any co-existing medical or psychiatric condition that is likely to interfere with study procedures and/or results

3.2 Screening Evaluation

This is a companion study to the therapeutic Phase II 5-FdCyd/THU study (NCI protocol # 09-C-0214: CTEP # 8351) and Phase I 5-FdCyd/THU study in Patients (NCI protocol # 12-C-0066/CTEP # 9127) open in the NCI Developmental Therapeutics Clinic at the Clinical Center, NIH. Both studies are multicenter studies and only patients enrolled at the Clinical Center will be recruited for this imaging protocol. After determination of enrollment on NCI protocol # 09-C-0214(CTEP# 8351) or NCI protocol # 12-C-0066/CTEP# 9127, patients will be approached for willingness to participate in this imaging study. To ensure eligibility for this imaging study, the following evaluation will be performed:

- 3.2.1 History and Physical Examination, including vital signs
- 3.2.2 Evaluation of Performance Status using the ECOG scale
- 3.2.3 β HCG or urine pregnancy test
- 3.2.4 Review of previous scans to assure measurable disease

3.3 Inclusion of Women and Minorities

Both men and women of all races and ethnic groups are eligible for this trial.

4 REGISTRATION PROCEDURES

Authorized staff must register an eligible candidate with NCI Central Registration Office (CRO) within 24 hours of signing consent. A registration Eligibility Checklist from the web site (<http://home.ccr.cancer.gov/intra/eligibility/welcome.htm>) must be completed and faxed to [contact]. After confirmation of eligibility at Central Registration Office, CRO staff will call Molecular Imaging Program ([name], MIP/CCR/NCI) to advise them of the acceptance of the patient on the protocol prior to the release of any investigational agents. Verification of Registration will be forwarded electronically via e-mail to the research team. A recorder is available during non-working hours.

5 STUDY IMPLEMENTATION

5.1 Study Design

Only patients who are enrolled in the therapeutic trials NCI Protocol # 09-C-0214 (CTEP# 8351) or NCI Protocol # 12-C-0066 (CTEP # 9127) will be recruited for this trial. The initial [F-18]-FdCyd + THU PET/CT imaging should be completed prior to therapeutic dosing. Repeat imaging will be performed 2-5 days after the initiation of FdCyd + THU therapy and at least 2 hours after dosing.

5.2 Study Schema

[figure not shown]
[figure not shown]

Figure 4: Imaging session without therapeutic “cold” FdCyd

[figure not shown]

Figure 5: Imaging session with “cold” FdCyd and administered per NCI protocol # 09-C-0214 (CTEP# 8351) and NCI protocol #12-C-0066 (CTEP #9127)

5.2.1 Imaging session per NCI protocol #09-C-0214 (CTEP #8351)

For THU administration, an IV bolus of 20% the total dose of tetrahydrouridine (total dose of THU = 350 mg/m²) is administered, followed by the other 80% of the dose, diluted in 250 ml of D5W, which will be infused for 3 hours or until the end of imaging. At least 20 minutes after the tetrahydrouridine IV is begun, the radiopharmaceutical will be administered over ~1 minute. The patient will be imaged continuously from top of head to thigh for 60-75 minutes, followed by whole body static imaging at 2 hours post infusion (approximately 2.5 hours total). A licensed clinical practitioner will be available during the drug administration and imaging session.

**The ¹⁸FdCyd will be administered at least 20 minutes after the THU is begun and concurrent with, or following (within 1 hr of) the start of the FdCyd therapeutic dose.

5.2.2 Imaging session per NCI protocol #12-C-0066 (CTEP #9127)

Patients will receive a dose of THU (total dose of THU is 3000 mg) for the initial scan approximately 2 hours (+30 minutes) before injection of the F-18 FdCyd radiotracer. The patient will be imaged continuously from top of head to thigh for 60-75 minutes, followed by whole body static imaging at 2 hours post radiotracer injection approximately 2.5 hours total). A licensed clinical practitioner will be available during the drug administration and imaging session.

5.3 Stopping Rules

For the purpose of protecting patient safety, the study will be stopped according to the following stopping rule.

Table 2

Number of Patients	Number of Grade 3 or 4 CTCAE toxicity
3-6	3
7-12	4
13-18	5

The operating characteristic of the stopping rule was assessed by simulations. Based on 10,000 simulations, the probability of stopping early for an excess of grade 3 or 4 CTCAE toxicity over the course of trial is 4.6% when the toxicity rate is 0.10 and 84% when the toxicity rate is 0.35. This is deemed reasonable for protecting patient safety.

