6.4 Protocol-Specific Expedited Adverse Event Reporting Exclusions

For this protocol only, AEs/grades that occur as a result of the therapy or participation in the parent protocol (NCI protocol # 09-C-0214: (CTEP# 8351) or NCI Protocol #12-C-0066: (CTEP# 9127)) are exceptions to the Expedited Reporting Guidelines and do not require expedited reporting (*i.e.*, CTEP-AERS). These AEs will be reported according to the expedited or routine reporting guidelines in NCI protocol # 09-C-0214 (CTEP# 8351) or NCI Protocol #12-C-0066 (CTEP# 9127).

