6.7 NCI-IRB Reporting

6.7.1 NCI-IRB Expedited Reporting of Unanticipated Problems, and Deaths

The Protocol PI will report to the NCI-IRB:

- All deaths, except deaths due to progressive disease
- All Protocol Deviations
- All Unanticipated Problems
- All serious non-compliance

Reports must be received by the NCI-IRB within 7 working days of PI awareness via iRIS.

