6.7.2 NCI-IRB Requirements for PI Reporting at Continuing Review

The protocol PI will report to the NCI-IRB:

1. A summary of all protocol deviations in a tabular format to include the date the deviation occurred, a brief description of the deviation and any corrective action.
2. A summary of any instances of non-compliance
3. A tabular summary of the following adverse events:
 - All Grade 2 **unexpected** events that are possibly, probably or definitely related to the research;
 - All Grade 3 and 4 events that are possibly, probably or definitely related to the research;
 - All Grade 5 events regardless of attribution;
 - All Serious Events regardless of attribution.

Abbreviated Title: [F-18] FdCyd Imaging

Version Date: 03-09-2015

Protocol Number: CTEP 8865, NCI 12-C-0014

NOTE: Grade 1 events are not required to be reported.

[figure not shown]

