11 STATISTICAL SECTION

The purpose of the study is to determine the safety of [F-18]-5-fluoro-2'-deoxycytidine (FdCyd) administered intravenously with administration of tetrahydrouridine (THU). As such, the sample size is targeted at 18 evaluable patients, which is adequate to assess the toxicity rate. With 18 evaluable patients, the width of the 80% expected confidence interval of 10% and 20% toxicity rate is 0.18 and 0.24, respectively.

To account for the possibility of a small number of inevaluable patients, the accrual ceiling is set at 20 patients.

Accruing approximately 1 patient/ month, this protocol is expected to be completed within 1.5 years.

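### The stopping rule in section 5.3 counts only Grade 3 or 4 toxicity, so a Grade 5 toxicity does not move the study's one numerical safety boundary (minor; wording fix)

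*Combined protocol and SAP*

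**What the plan says.** Section 5.3 says the study will be stopped according to Table 2. The table sets the number of patients (3-6, 7-12, 13-18) against the "Number of Grade 3 or 4 CTCAE toxicity" (3, 4 and 5). The text below it keeps the same grades: from 10,000 simulations, "the probability of stopping early for an excess of grade 3 or 4 CTCAE toxicity over the course of trial is 4.6" percent at a toxicity rate of 0.10, and 84% at a rate of 0.35.

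Elsewhere the protocol treats Grade 5 as distinct from Grades 3 and 4:

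- Section 6.3.3 (Table 3) sets a joint timeframe for serious Grade 3-5 events, with a first report within 24 hours.
- Section 6.7.1 sends to the IRB "All deaths, except deaths due to progressive disease".
- Section 6.7.2 lists "All Grade 3 and 4 events that are possibly, probably or definitely related to the research" and, as a separate item, "All Grade 5 events regardless of attribution".
- Section 12.3 requires adverse events to be reviewed after every case, with a decision on going on to the next participant.

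None of these sections refers to Table 2 or adds to its count. Section 11 sets the target at 18 evaluable patients, "which is adequate to assess the toxicity rate".

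**The concern.** Safety of the tracer given with THU is the first primary objective (section 1.1.1), and Table 2 is the only numerical boundary that protects it. As worded, the most serious grade is the one severe grade that does not bring the study closer to stopping. The literal reading is not far-fetched: sections 6.3.3 and 6.7.2 show that where the protocol means to include Grade 5, it says so. The stated stopping probabilities describe a rule for the counted grades only, so protection against severe toxicity as a whole is lower than 84% to the extent that some severe toxicity is fatal.

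**Working it through.** **Inputs.** Boundaries, rates (0.10, 0.35) and stated results (4.6%, 84%) are from section 5.3; the maximum of 18 patients is from section 11; two imaging sessions per patient are from section 2.1.4.

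**1. Reproduce the plan's figures.** Treat each patient as one yes/no outcome with probability p, and let S(n) be the number of affected patients after n. Stop when S(n) ≥ b(n), with b = 3 for n = 3-6, 4 for n = 7-12 and 5 for n = 13-18. Among paths that have not stopped,

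P[S(n) = s] = (1 − p)·P[S(n−1) = s] + p·P[S(n−1) = s − 1],

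and the probability on s ≥ b(n) is added to the stopping total at each n.

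The first segment can be done by hand, because the count never falls and so stopping by patient 6 is the same as S(6) ≥ 3. At p = 0.10: 1 − (0.9⁶ + 6·0.1·0.9⁵ + 15·0.1²·0.9⁴) = 1 − (0.5314 + 0.3543 + 0.0984) = 0.0159. Carrying the recursion on to patient 18 gives:

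| Rate p | Exact | Stated |
|---|---|---|
| 0.10 | 4.64% | 4.6% |
| 0.35 | 83.5% | 84% |

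Both agree within simulation error: with 10,000 runs the standard error is about 0.2 and 0.4 percentage points. Stopping only when the count exceeds the boundary would give 0.9% and 66.3%, so the rule stops at the boundary.

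**2. Counting example.** Six patients: two with Grade 3/4 toxicity, one with Grade 5, three with neither. The literal count is 2 and the boundary is 3, so the rule is not met. Counting Grade 3 or higher gives 2 + 1 = 3, and the rule is met. No assumed rate is needed.

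**3. Effect on the stopping probability.** Let r be the per-patient rate of Grade 3-5 toxicity and g the share of affected patients whose only severe toxicity is Grade 5. Table 2 then sees the rate r(1 − g). The documents give no value for g, so a range is assumed. The recursion of step 1 with r = 0.35 gives:

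| g (assumed) | Counted rate 0.35(1 − g) | P(stop) |
|---|---|---|
| 0 | 0.3500 | 83.5% |
| 5% | 0.3325 | 79.5% |
| 10% | 0.3150 | 74.8% |
| 20% | 0.2800 | 63.8% |
| 30% | 0.2450 | 50.9% |

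**4. Unit of the count.** Step 1 shows that the stated figures use one outcome per patient. For comparison, suppose events are counted over two independent sessions with the patient-level rate held at p. The per-session rate is q = 1 − √(1 − p): 0.0513 at p = 0.10 and 0.1938 at p = 0.35. A patient contributes 0, 1 or 2 events with probabilities (1 − q)², 2q(1 − q) and q². The stopping probabilities are 5.8% and 87.4%, against 4.64% and 83.5%.

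**The case against.** The strongest reply is that a death could not pass unnoticed. Section 12.3 requires a decision after every case, section 6.3.3 requires rapid reporting of serious Grade 3-5 events, and sections 6.7.1 and 6.7.2 bring deaths and Grade 5 events to the IRB. That stands, and a reader who inferred that a death would be ignored would be wrong. What remains is that these are review and reporting steps; none of them moves the boundary. It is also fair that the tracer is a microdose for which, by section 2.1.3, "no toxicity is expected to be observed from the radiopharmaceutical", so the counting example describes an unlikely course and the upper fatal shares are illustrative.

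Three stronger readings are tempting but not supported.

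- *The stated probabilities are wrong.* They reproduce.
- *The unit is undefined, so the operating characteristics are unknown.* Table 2 does not name the unit, but the toxicity rate, the sample-size reasoning in section 11 and the reproduced figures all point to patients. The independent-session variant shifts the result by little more than one point at 0.10 and about four at 0.35. Larger shifts need fractions of patients with several events that the documents do not supply.
- *Toxicity from the parent therapy counts towards the boundary.* Section 5.3 does not state attribution, but section 2.1.3 uses toxicity in a causal sense and section 11 ties the rate to the safety of tracer plus THU. Section 6.4 says of parent-therapy events: "These AEs will be reported according to the expedited or routine reporting guidelines in NCI protocol" (the parent protocols); it governs reporting only, but points the same way. Counting all causes would also be a defensible conservative choice. The documents give no background rate for the one-day monitoring window (section 6.1.1), so the size of any distortion cannot be derived.

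**Conclusion.** The point holds for Grade 5. As written, the only numerical boundary leaves out fatal toxicity, and no other section repairs this. The counting example rests on the wording alone. The fall from 83.5% to between 79.5% and 50.9% rests on an assumed fatal share of 5-30%, on a 35% Grade 3-5 rate, on 18 patients, and on the fatal event being the patient's only severe one. The unit should be written down, but it is the unit the stated figures already imply. Attribution is a minor clarification, not a demonstrated error. Because case-by-case review and reporting would still catch a death, and the repair is a change of wording, the severity is minor.

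**What to change.** In section 5.3, reword the Table 2 column and the text below it to *number of patients with at least one Grade 3 or higher (including Grade 5) CTCAE toxicity*, and state that 0.10 and 0.35 are per-patient rates of Grade 3 or higher toxicity. The restatement is needed because the text now attaches those rates to Grade 3 or 4 only; once it is made, the boundaries and the 4.6% and 84% stay as they are. The same wording settles the unit as patients.

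Add one sentence saying whether the count is limited to events at least possibly related to the imaging agents (section 6.2 already has the attribution categories) or covers all causes.

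The cost is an amendment of wording: no added patients, procedures or simulations. If the count is limited by attribution, the repeat session will still need judgement. The tracer is chemically identical to the therapeutic drug (section 2.1.4), and cold FdCyd is given around that scan (section 8).
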